Focus groups	T10-T12	
We will send information about the focus groups to the practitioners via the Kitbag super lead and then purposively sample aiming for a heterogenous sample of practitioners from different team types and of different roles.
 
For the focus group discussions for the super leads, all will be invited to attend.

Interviews (n=16)	T10-T12	
Children: Practitioners who attend the focus group discussion will be asked to identify children on their caseload who may be open to participating.
 
Foster carers: the Kitbag leads in the fostering teams will be asked to send information about the interviews to the foster carers. We

		will purposively sample aiming for a heterogenous sample of foster carers of children of different ages.
Survey (assume 10% response rate)	T1 T13	A survey will be shared with all staff (i.e. no sampling) across intervention and comparator teams: 
 • Social workers and family support workers (includes Kitbag Leads) • Inhouse foster carers (the survey will be adapted slightly for this group) • Team Managers
Observations of workshops (n=4)	T3-T4	A researcher or research assistant will observe at least one workshop per local authority.

Analysis

Qualitative data preparation and analysis of interview and observational data

Interviews will be recorded, transcribed and pseudonymised prior to analysis. Qualitative analysis of interview and observational data will use NVivo software and follow a thematic analysis approach. This will involve data familiarisation, checking accuracy of transcription, labelling the data with descriptive codes and developing themes which describe patterns across the data to answer the pre-specified research questions. Analysis will look for patterns, consistencies and inconsistencies across different informants and time points that might be informative for the research questions.

The following steps will be taken to ensure rigor in the analysis and reporting of qualitative data:

- Confidence that the findings are an accurate reflection of participant experience will be ensured through presentation of examples of participant responses using quotes, and triangulation between different informants and data collection methods.
- The degree to which findings are transferable to other contexts will be considered through detailed description of contextual factors, and collection of data from a range of informants to gather a range of perspectives.
- Transparent reporting of the research and analysis process will ensure the study methods are clear and repeatable.
- When interpreting findings, consideration will be given to contrasting and inconsistent accounts.
- Qualitative data analysis will be overseen by WWCS's Senior Qualitative Researcher.

Quantitative analysis of survey and administrative data

Quantitative data will be analysed descriptively, in order to present characteristics of delivery and acceptability. The results will be triangulated with the qualitative findings by looking for consistencies and inconsistencies between the different data sources.

Cost evaluation

Whose costs

We consider the costs from the perspective of the local authorities if they were to implement the programme themselves. We shall report the total costs for each local authority and the costs per family (total costs / (total caseload for treated teams at the beginning of the intervention + the total caseload who start within the intervention period)).

We do not consider costs to families. The use of the Kitbag will be during their usual sessions with social workers and family support workers so there is no additional cost to them in terms of time or otherwise.

What costs

Given that the programmes team of WWCS is funding the programme, we shall request the budget submitted to them from the intervention developers. We shall include all costs related to the provision of the programme (but not the development) broken down by the following categories:

- **Kitbags** for social workers and family support workers in the treated teams. Kitbags for foster carers and kinship carers of the children supported by these teams. An additional 15% of the total Kitbags required to allow for staff turnover (permanent staff can take their Kitbag with them) and an additional 10% for foster / kinship carers (due to placement change and / or carer turnover).
- **Access to Kitbag Online** (if a licence is required)
- **Distribution of Kitbags**
- **Workshops by the intervention developers**
- **Support for using Kitbags other than the workshops**
- **Other costs associated with delivering the programme**

Additionally, we shall ask the local authorities (via a survey to the local authority lead contact) if they incurred any additional costs associated with the programme e.g.:

- **Resources:** the replacement of lost or empty items from Kitbags; additional resources for the workshops
- **Personnel:** the cost of hiring agency workers to conduct day-to-day work so that social workers / family support workers could attend the workshops (if applicable)
- **Administration costs:** the cost of hiring additional staff to administer the programme

The costs will be reflective of the current context of Covid-19 restrictions. In some cases, this is likely to increase the costs e.g. distribution, and in other circumstances, it's likely to decrease the costs e.g. virtual workshops instead of in-person workshops.

Where there is additional work required but not sufficient to hire an agency worker or another member of staff, we shall report the additional time commitment in hours over the course of the year for the staff affected.

As well as these costs incurred over the duration of the programme, we shall report prerequisites (anything the local authority needed to run the programme but may already have e.g. laptops) and expected ongoing costs. Costs associated with the development of the programme and the evaluation e.g. the collection of data will be excluded.

Valuing benefits and disbenefits

Although administrative outcomes aren't the outcomes of most interest, we only include the administrative outcomes when valuing benefits as these are the benefits that are "cashable" to local authorities:

- De-escalation in children's social care status as a benefit
- Escalation in children's social care status as a disbenefit
- Number of social worker sick days averted (estimated by the coefficient on treatment in the regression of the number of days attended on treatment and covariates)

For the impact evaluation, we code de-escalation and escalation as a single outcome. But because there are different costs associated with each movement, we shall separately estimate the impact of Kitbags on the likelihood of moving between different levels of CSC intervention. For each movement, we calculate the total monetised benefit:

- Unmonetised benefit = ATE (i.e. the coefficient on the treatment dummy) x number children randomised to the intervention group
- Monetised benefit: total unmonetised benefit x cost (averted) / child

The outcomes do not double count any benefits and we only include outcomes that are significant at the 5% level. We request data from the local authorities on the average costs of supporting a child at each level of CSC intervention and use this to determine the "cost (averted)" value. Whilst placement costs vary, we use an average for simplicity. We sum the monetised benefits and disbenefits to arrive at a net benefit.

We do not monetise the other outcomes such as improved behaviour amongst children and young people. This is not to say that these outcomes aren't valuable but simply that there's less agreement on how to put a monetary value on these outcomes. We report a list of outcomes that are significant.

Discounting

Given that all the benefits and costs occur within the same financial year, we do not discount any of the benefits or costs.

Reporting

We report the benefit-cost ratio, and the net present value per child.

Ethics & Participation

An ethics application for this evaluation was submitted to WWCS's research ethics committee on 25th February 2021 with a favourable opinion given on 23rd March 2021.

Consent procedures

Information sheet contents

The information sheets will be tailored to the participant group and will detail the purpose of the project, why they have been invited to take part, what will happen if they take part, whether they have to take part, the possible risks, the possible benefits, the data handling, confidentiality and data protection, the right to withdraw their consent, how the project is funded, what will happen to the results of the project, contact details if they wish to ask further questions.

Social workers

Data collection from social workers will be via an online survey. The first page of the survey will be an information sheet and consent elicitation.

Impact Evaluation: Secondary Data Collection

Children and young people

Pseudonymised administrative data on interactions with children's social care (CIN plans, CPP, CLA and case closure) will be requested from local authorities. Consent for the sharing of this data will not be explicitly sought from families. This is because we consider the risk to participants arising from the sharing and processing of this data for the purpose of the evaluation to be very low, and the benefit to accessing the data for all eligible participants to be high. The risk that the eligible participants are identified is very low, and the risk of a data breach will be carefully managed so that it remains low. The benefit of accessing the data for all eligible participants is that we maintain statistical power and reduce the risk of selection bias into the sample, allowing for better - unbiased and more precise - estimates of the treatment effect, making the evaluation much more useful to decision-makers. Having said this, participants will be able to withdraw their consent for their data to be processed for the evaluation if they so choose to via a form on the WWCS website. Please see the Data Protection section below for more details on the data governance of this.

Social workers and family support workers

Pseudonymised administrative data on the sickness absence of social workers and family support workers will be requested from local authorities. Consent for the sharing of this data will not be explicitly sought from social workers for the same reasoning as above.

Summary statistics about access to Kitbag Online will be requested from IFF. Given that the social worker participants will not have accessed the website before, it may be possible to add consent to share for purposes of the evaluation into the terms of use. We are currently investigating this with the delivery partners.

Implementation and process evaluation

Focus group discussions and interviews

Focus group discussion and Interview participants will be sent an information sheet in advance of the interview. Before the interview commences, the researcher will ask the participant if they have read and understood the information sheet, and whether they have any questions. The researcher will then elicit consent for participation and for the interview to be recorded. When eliciting consent for participation in interviews, researchers will make clear the limits of confidentiality (See Section D for further information).

Observation

Researchers will observe a subset of the workshops conducted by the intervention developers. The attendees of the workshops are social workers and family support workers in the treated teams. The number of participants in each workshop is quite large (approximately 25) and so it would be difficult to seek verbal consent from all participants. Workshops attendees will receive an information sheet explaining that the workshop will be observed as part of the evaluation and be given the opportunity to ask any questions. At the beginning of the workshops, those running the workshops will inform attendees about the observation and introduce the researchers who are observing. The attendees will be informed that:

- The sessions will not be recorded (for evaluation purposes at least);
- The coding frame will be designed such that attendees will not be identifiable;
- (In the likely case that the workshops will take place virtually) attendees can keep off their camera and microphone if they chose to.

Although there is a risk that declining to be observed affects participation in the workshop, we think that this is relatively low risk (as participating in any group setting involves being observed by others to a certain extent).

Withdrawal of consent

Any participant who would like to withdraw their consent to participate and for their data to be processed (alongside exercising any other rights guaranteed under GDPR) can use a form on

the WWCS website. The email invitation to the survey for social workers and family support workers will include a link to the page containing the form so that participants can easily find it after completing the survey. The email invitation will also include contact details of the evaluators so that participants can submit a request to withdraw consent directly via email also. We anticipate that if a CYP or parent / carer wishes to withdraw, their social worker can assist them to WWCS. We provide instructions to social workers on how to do this in an FAQ document. The participants will be able to request for their data to be deleted up until the analysis and reporting stage of the project (June 2022).

Risks of the data collection activities:

- **Time burden on social workers:** According to an [April 2020 Community Care survey](#), about 70% of the social workers who responded found their caseload “completely unmanageable” or “hard to manage”. We also appreciate that at the current time social workers may be taking on additional work due to Covid-19 (colleagues being sick or shielding, withdrawal of multi-agency partners from conducting home visits, supporting CYP to return to school). Adding to the burden on social workers could have knock-on effects for the families they support in leaving less time for direct work. To reduce the burden as much as possible on social workers, we only ask them to collect the data themselves for new CYP entering services (rather than all CYP with an open case) For those with open cases, we ask them to introduce the evaluation and encourage the parents / carers to participate. In our power calculations, we assumed a 15% rate of parents / carers consenting to be involved in the evaluation. Although we will ask social workers to try to recruit all families (otherwise there is a risk of selection bias into the sample); a conservative estimate of the success rate takes into account the other pressures on their time.

Registration

The trial has been pre-registered on the OSF website: osf.io/zmtus and published on WWCS’s website. The OSF pre-registration will be updated with the final report at the end of the evaluation.

Data protection

We have prepared a data privacy impact assessment for the project, which has been approved by WWCS’s Director of Operations. Please find the link to the data protection notice published to our website [here](#).

Purpose of data processing

The aim of this research is to:

- evaluate the impact of Kitbags on the emotional resilience of children and young people with a social worker (and secondary outcomes for CYP, parents, social workers and foster carers)
- evaluate how the programme is implemented in a social care setting (and during Covid)

The expected benefit of conducting the research is to provide evidence on whether Kitbag “works” in a children’s social care setting, and so feed into decision-making of senior leaders in CSC. A secondary benefit is for the findings to feed into the further development of Kitbag.

Categories of personal data

We expect to process:

- Pseudonymised data for c. 13,000 children and young people, c.1000 social workers and c.1000 foster carers

The processing of pseudonymised data involves storing it and conducting analysis on it. The pseudonymised data will contain special category data including ethnicity and health (disability) data. It will also contain data which is not special category but highly sensitive e.g. children's social care status.

The geographical coverage is CYP supported by children's services in four local authorities (a small proportion may be in placements outside of those local authorities' boundaries). The data includes data about children, in particular vulnerable children. The approach is not novel and there are no issues of public concern.

Roles of key parties

WWCSC will be the controller for the primary and secondary data collected.

Legal basis

We rely on different legal bases for different processing activities. Please see the Privacy notice²² (p.4) for full details.

We will process some special category data, namely ethnicity and health (disability status). The conditions for special category data is archiving, research and statistics.

Data transfers

We shall request for all personal data to be sent via Egress or an equivalent platform of the local authorities' choice.

Storage

For the duration of the project (until Summer 2022), data will be stored on a dedicated drive only accessible to the project team in line with WWCSC's data protection policy. The access will be controlled by WWCSC's access control policy.

Intention to archive data

As with many of our other projects, we anticipate that the data shall be transferred to our secure data archive. This archive is hosted and stored by the Office of National Statistics ("ONS") 'Secure Research Service' on our behalf, we are the data controller and access to any data stored within the archive is therefore controlled by the ONS and WWCSC. We shall ensure that we have all necessary rights, notices and/or consents in place in order to transfer such personal data to us for this purpose. The location of the archive is to be confirmed, we anticipate it will be held by the Office for National Statistics 'Secure Research Service'. The duration of retention is indefinite.

Personnel

Delivery team:

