There has been no additional adaptation of the Kitbag itself from the school setting but the support is tailored to the social work setting, focusing on the relationship-based and reflective practice skills of the social workers and their role in leading the shift in practice within their teams.

As mentioned above, we expect that the version of the programme trialled will involve considerably more use of the Kitbag Online than in non-Covid-19 times. We attempt to address the generalisability of the findings in the implementation and process evaluation (please see below).

Logic model

* indicates outcomes that will be measured.

Impact Evaluation

Research questions

Primary research questions

Child outcomes:

- Primary outcome 1: What is the impact of the “Putting the Kitbags to work” programme on the number of **escalations and de-escalations** of eligible children supported by social workers? The comparison is between eligible children supported by social workers in teams randomly allocated to the intervention arm compared with eligible children supported by social workers in teams randomly allocated to the control arm within the intervention period.
- Secondary outcome 1: What is the impact of the “Putting the Kitbags to work” programme on the **behaviour** of eligible children supported by social workers? The comparison is between eligible children supported by social workers in teams randomly allocated to the intervention arm compared with eligible children supported by social workers in teams randomly allocated to the control arm. The outcome will be measured by the total difficulties score of the Strengths and Difficulties Questionnaire. The population will be restricted to children who’ve been looked after continuously for 12 months or more whose SDQ has been assessed from T4 - T12.

Social worker outcomes:

[figure not shown]
- Secondary outcome 2: What is the impact of the “Putting the Kitbags to work” programme on the **self-efficacy** (as measured by the competency subscale of the Work-Related Basic Needs Satisfaction scale) of social workers and family support workers in teams randomly allocated to the intervention arm compared with social workers and family support workers in teams randomly allocated to the control arm? The outcome will be measured at month 6 and month 13 after intervention began.

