Children's cases can "escalate" to increased involvement (+1 for each step), stay the same (0) or "de-escalate" to lower levels or no involvement (-1 for each step). If the child's case closes and then another is opened, we would count that as an escalation. We consider a decrease in CSC involvement a positive impact.

Secondary Outcomes

2i) Emotional and behavioural difficulties

The Strengths and Difficulties Questionnaire (SDQ) is a brief emotional and behavioural screening questionnaire for children and young people. The SDQ has been tested in large samples (10,000+) with a variety of age ranges (4-17 years old). It has satisfactory to strong internal consistency (Cronbach's alpha of 0.73⁹, 0.81¹⁰), moderate test-retest reliability (Pearson's coefficient of 0.71 over an 8-week period¹¹), good concurrent validity (e.g. a

⁹ Goodman. R. (2001). Psychometric properties of the strengths and difficulties questionnaire. *Journal of the American Academy of Child and Adolescent Psychiatry*, 40 (11), 1337-1345.

¹⁰ Yao, S., Zhang, C., Zhu, X., Jing, X., McWhinnie, C. M., & Abela, J. R. Z. (2009). Measuring Adolescent Psychopathology: Psychometric Properties of the Self-Report Strengths and Difficulties Questionnaire in a sample of Chinese adolescents. *Journal of Adolescent Health*, 45, 55-62.

¹¹ Yao, S., Zhang, C., Zhu, X., Jing, X., McWhinnie, C. M., & Abela, J. R. Z. (2009). Measuring Adolescent Psychopathology: Psychometric Properties of the Self-Report Strengths and Difficulties Questionnaire in a sample of Chinese adolescents. *Journal of Adolescent Health*, 45, 55-62.

Pearson's coefficient 0.7 for the correlation between SDQ total difficulties score and Child Behaviour Checklist total score) and good discriminatory validity of the subscales¹². The SDQ is recorded annually for children in care and so is a familiar measure to at least a subsample of the participants in the intervention. The SDQ has been used in over 4000 research studies¹³.

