We measure this outcome through a decrease in the total difficulties score of the SDQ (the sum of the emotional, peer, behavioral and hyperactivity subscales - all except the prosocial score as scored according to the instructions by the SDQ developers¹⁴). The score ranges from 0 to 40 with a lower score representing better behaviour. Although the individual subscales appear to measure distinct concepts in high total difficulty score populations (like children with a social worker)¹⁵, we use the total difficulty score instead of the individual subscales to reduce measurement error.

For this outcome, the population is restricted to children who've been i) continuously looked after for 12 months or more and ii) who have used Kitbag for four months or more at the time of their SDQ being assessed. i) is the population for whom SDQs are available in administrative datasets and we further restrict this population to ii) to allow for the minimum number of uses of the Kitbag.

Social Worker and Family Support Worker Outcomes

2ii) Social worker / family support worker self efficacy

As represented in the logic model, one of the hypothesised mechanisms is that social workers feel they have the tools to do their job well. We shall measure whether Kitbag improves social workers' self-efficacy through the competence subscale of the Work-Related Basic Needs Satisfaction scale. The competency subscale is a 4-item scale which respondents agree or disagree on a 5-point Likert scale with good reliability (a Cronbach's alpha of .85), and reasonable predictive validity (correlates positively with job satisfaction and vigour, and negatively with exhaustion)¹⁶. The fourth secondary outcome measure is the mean of the responses for the 4 items where "totally disagree" is coded as 1 and "totally agree" is coded as 5 (2iv).

2iii) Stress

As represented in the logic model, one of the hypothesised mechanisms is that social workers feel more valued by the local authority and feel better supported by their team, reducing their stress. Social worker stress will be measured by the 7-item "Stress in General" scale which has good reliability (above 0.7) and good convergent validity (it correlates negatively as expected with job satisfaction and positively with intention to quit)¹⁷. Higher scores represent

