- for social workers and family support workers: the social worker or family support worker was a member of a team assigned to the intervention at point of randomisation and 0 else;
- for foster / kinship carers: the carer cares for a child or young person whose case is held at the point the foster carer enters the sample, by a social worker who is a member of a team assigned to the intervention at point of randomisation and 0 otherwise.

Although there is some turnover of social workers, family support workers and foster carers, about 80% of those at T0 (April 2021) will still be working with the local authority at T13 (May 2022), and so 80% will have received the full 12 months of the intervention. Binarising the treatment seems a reasonable proxy in this case.

For the outcomes relating to children, treatment is coded as a binary variable. When children enter the sample, at either the point of randomisation, or the point they become eligible (e.g. their case opens and meets other criteria) they will be allocated to treatment if the team of their allocated social worker was randomised to treatment.

Covariates

Including control variables increases the precision of the estimate. In each regression, we control for a number of relevant covariates. We outline different categories of covariates below.

Site effects

We include site fixed effects but not site-treatment interaction terms.

Previous outcome measures

We control for the previous measurements of the outcome variable where data is available. For the survey-based measures for social workers, family support workers and foster carers, the same measures will be asked at T6 (October 2021) and T13 (May 2022), and for administrative data we expect previous values to be available. For the outcomes of the CYP and parents / carers (including kinship carers), the previous measure of the outcome will be at T0 (April 2021) or when they entered services if they entered services after T0 (April 2021).

Other covariates

For CYP outcomes (primary outcome i) and secondary outcome i)), we include the following vector of individual-level covariates:

- gender (coded as male, female, or other/missing)
- age group (4-11, 12-17, 18 years, or missing with 4-11 as the reference category)
- ethnicity (Asian / Asian British, Black / African / Caribbean / Black British, Mixed / Multiple ethnic groups, Other ethnic group, White, missing; with the majority group as the reference category)

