- For each outcome, we will regress an indicator of missingness on the covariates in the main model (see the “Covariates” section) using logistic regression with standard errors clustered at the team level. If any of the coefficients on the covariates of the missingness model are statistically significant at the 5% level, then data is not missing completely at random (MCAR).
- In particular, we are interested in the coefficient on the treatment dummy. If it is not significant, this suggests that the data is missing experimentally at random (MEAR) (where data may be correlated with observable or unobservable variables, but not with treatment assignment) and we will only include observations for which we have the outcome data controlling for any variables which are significant (if they are not already specified in the “Covariates” section above).
- In line with WWCS statistical guidance, if the data on outcomes is missing experimentally not at random (MENAR) e.g. due to large differential attrition, then we will multiply impute within the treatment condition.

Sensitivity analysis following multiple imputation

Given that there may be a substantial proportion of outcome data to impute, we check the sensitivity of our results to the imputation strategy. We will:

²¹ See Taljaard, M., Donner, A., & Klar, N. (2008). Imputation strategies for missing continuous outcomes in cluster randomized trials. *Biometrical journal. Biometrische Zeitschrift*, 50(3), 329–345. <https://doi.org/10.1002/bimj.200710423>

- impute using baseline observation carried forwards (BOCF)
- impute using control drifted observation carried forward (CDOCF). This is done by carrying forward the baseline observation and then adding the “drift” from the comparator group to take into account the amount their outcome would have changed in the absence of treatment. The drift is calculated using an autoregression model for the comparator group.

Reporting

In addition to handling missing data and conducting sensitivity analyses, we also report some summary statistics to allow for a qualitative assessment of the impact of missing data on the treatment effect estimate.

- For each outcome and covariate, we will report the percentage of missing data alongside summary statistics
- Rates of loss to “post” data collection for the arms of the trial

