January 2021	Advisory Board meetings	UoS/IFF
January - March 2021	Site selection, engagement, set up meeting and work	All
March 2021	Ethics approval obtained	WWCS
March 2021	Randomisation of teams to kitbag	WWCS
April 2021	Kitbag leads identified and appointed	LA partners
Before data collection	Trial protocol drafted and published	WWCS
May 2021	Kitbag distribution	UoS/IFF

10th May 2021	Launch of project in 4 sites as one online event	UoS/IFF + LA partners
May 2021 - April 2022	Regular Kitbag use	LA partners
May 2022	Endline data collection	LA partners / WWCS
June - July 2022	Final analysis and report	WWCS

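### The SDQ analysis admits only children who have an SDQ recorded after randomisation, so the plan's own missing-outcome rule cannot act on that outcome

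*Protocol*

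**What the plan says.** Two sections define who enters the SDQ (total difficulties) analysis.

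- Research questions, Secondary outcome 1: children "looked after continuously for 12 months or more whose SDQ has been assessed from T4 - T12".
- Outcome measures, 2i: children in continuous care for at least 12 months "who have used Kitbag for four months or more at the time of their SDQ being assessed". The first condition is explained by data availability: it "is the population for whom SDQs are available in administrative datasets".

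The same section notes that "The SDQ is recorded annually for children in care".

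Missing data strategy, Outcomes, sets one rule for all outcomes: "For each outcome, we will regress an indicator of missingness on the covariates in the main model". If the treatment coefficient is not significant, only observed outcomes are analysed. If missingness differs by arm, outcomes are multiply imputed within arm. Handling non-compliance promises intention to treat for all analyses, with a child's arm fixed on entry to the sample whether or not Kitbag is used.

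No section gives an SDQ denominator fixed at baseline, or says what happens to children who leave care before their SDQ or are not assessed.

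**The concern.** A population defined by possession of the outcome cannot have missing outcomes. A child in care at T0 who goes home before the annual SDQ, or whose SDQ is not completed, is not lost from the analysis; on paper the child was never in it.

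This matters because leaving care is a de-escalation, which the primary outcome scores as benefit. If the programme changes who stays in care, or whose SDQ gets completed, the two SDQ groups are selected differently, and the safeguard written for that situation is switched off.

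The Kitbag-use condition in 2i is a separate fault. Control teams receive no Kitbags, so read literally no control child qualifies. It also makes use of the intervention an entry criterion, against the intention-to-treat rule.

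**Working it through.** **Dates.** The timeline puts "Randomisation of teams to kitbag" in March 2021, and T0 is April 2021. T4 to T12 is therefore August 2021 to April 2022, all after allocation. Twelve continuous months in care by T12 means care began by about T0; by T4, by about August 2020. Entry to care is thus essentially a baseline matter. The post-randomisation parts are staying in care until the SDQ and being assessed in the window.

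**The missingness test.** In the population as worded, the indicator is 0 for every child, so the logistic regression has no events and its treatment coefficient is not identified. With a denominator fixed at T0 and assumed loss of 20% (control) and 30% (intervention), the coefficient exists: ln[(0.30/0.70)/(0.20/0.80)] = 0.54.

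**Possible bias, unadjusted.** Assume no true effect, SDQ in SD units, and a latent tendency to stay and be assessed that correlates r with a higher SDQ. With p the proportion retained and z = Φ⁻¹(p):

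bias = r × [φ(z_T)/p_T − φ(z_C)/p_C]

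The ratio φ(z)/p is 0.350 at p = 0.80, 0.424 at 0.75, 0.497 at 0.70 and 0.720 at 0.55.

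| Loss, control vs intervention (assumed) | Bracket | r = 0.2 | r = 0.5 |
|---|---|---|---|
| 20% vs 25% | 0.074 | 0.015 | 0.037 |
| 20% vs 30% | 0.147 | 0.029 | 0.073 |
| 30% vs 45% | 0.223 | 0.045 | 0.111 |

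With equal retention the bracket, and so the bias in this model, is 0.

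**Possible bias under the planned model.** The child regression includes the previous SDQ, and the sample-size section expects baseline to explain 0.8 of endline SDQ. I simulated the same model with baseline SDQ in the OLS.

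- Loss depends on baseline SDQ: bias is about 0 in every scenario.
- Loss depends on follow-up SDQ, R² = 0.8: about 0.005 to 0.024 SD over the lower two rows. As a check, (1 − 0.8) × 0.029 = 0.006 and (1 − 0.8) × 0.111 = 0.022.
- Loss depends on follow-up SDQ, assumed R² = 0.5: about 0.015 to 0.06 SD.

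**The stated MDES.** The formula for the named design, with 60 teams of 150, ICC 0.03, R² 0.8 (child) and 0.1 (team), and 4 × (15 − 2) − 3 = 49 degrees of freedom, gives 2.859 × √[0.03 × 0.9/(0.25 × 60) + 0.97 × 0.2/(0.25 × 9000)] = 0.124, against the stated 0.127. That figure is for 9,000 children. Table 1 lists 14 CLA and 10 disability teams. If the SDQ children sit mainly in those 24 teams (an assumption), the same formula with 24 − 8 − 3 = 13 degrees of freedom gives 0.21 at 150 children per team and 0.27 at 10.

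**The case against.** The strongest reply is that the size is small under the analysis actually planned. Baseline adjustment removes bias that acts through baseline difficulty and cuts the rest to about a fifth at R² 0.8. This stands, with one limit. Adjustment applies only where a previous SDQ exists, and by the Protocol's own account administrative SDQs exist only for children with 12 months in care. Children who first reach 12 months during follow-up may have none, and a covariate with more than 30% missing is dropped.

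Several stronger readings are tempting, and the Protocol does not support them.

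- *The plan would show no sign of attrition.* The primary outcome compares de-escalation in all eligible children, the Dosage section regresses duration of social care involvement on treatment, and loss to post-intervention data collection is reported by arm. These could give indirect signals, but none is tied to the SDQ denominator.
- *Kitbag would be made to look harmful.* That needs lower-difficulty children to be lost, and more of them in the intervention arm. Nothing indicates which children go unassessed, so the direction is unknown.
- *The bias approaches the detectable effect.* The 0.127 does not apply to this subset.
- *Half the children will be lost.* The 50% exit figure covers all children in services, not those in care.

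The restriction to 12 months in care is also a fair response to data availability. And a child who leaves care after an SDQ in the window stays in the analysis.

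**Conclusion.** The point holds as one of definition. As worded, an SDQ recorded after randomisation is an entry condition, the missing-outcome rule cannot operate on this outcome, and the Kitbag-use condition excludes control children and contradicts intention to treat.

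Bias is a risk, not a certainty, since it needs retention or assessment to differ by arm. Its plausible size runs from about 0 to 0.024 SD with baseline adjustment at R² 0.8, through about 0.06 SD at R² 0.5, to 0.03 to 0.11 SD if no usable baseline SDQ is available. The loss rates, the correlations and the R² of 0.5 are assumptions; the Protocol gives no retention or assessment rate for children in care. The case for change is less the expected size than that the plan could not tell whether the problem had occurred, on its only remaining direct measure of child behaviour.

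**What to change.** 1. Define the SDQ population at T0 by the team's allocation: children in care in an eligible team whose care episode began early enough to reach 12 months by T12, whatever happens later. Since 12 months by T12 requires care from about T0, this excludes almost nobody who could have qualified.
2. Replace the Kitbag-use condition in 2i with the same calendar window in both arms, and reconcile 2i with Secondary outcome 1.
3. Report four exclusive groups by arm: SDQ in the window; SDQ only in T1 to T3; left care before assessment; in care but not assessed. The second group is outside the window by schedule. T4 to T12 covers 9 of the 12 months, so with evenly spread annual assessments (assumed) it would be about 25%. It should not be mixed with true losses.
4. Treat the last two groups as missing and apply the existing missing-outcome rule to them.

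The cost is wording, plus a list of children in care at T0 with care start and end dates, which should be obtainable from the administrative data already being requested. The downside is a visible missing-data rate and some imputation.
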